Appendix A. Binder Forms

Site: _____

Implementation Team Details

Staff Name	Position	Did individual complete EFCT?	Email address*	Did individual watch both IPPI training videos?	Did individual review 3 tip sheets (Considerations before, during and ending the IPPI)?

***email address will be used to identify if individual completed the Emotion Focused Communication Training**

IPPI Program – Resident Preferences Worksheet

Site champion(s) will maintain a password protected list of the name of each resident that is enrolled into the IPPI program along with a unique ID# that is determined by the champion(s). This password protected file will be shared with the PI who will then link the data from this worksheet to the electronic medical record data prior to deidentifying.

After completing a resident's preference assessment, identify and record their most important preferences in the column "Important Preferences." Next, review the list of IPPI protocols then record the protocols that match the resident's important preferences in the "Matching IPPIs" column. Review the list of matching IPPIs with the implementation team member(s) that will be facilitating the activity with the resident and let them chose which IPPI activities (1-2) they are most comfortable doing. After they've chosen the IPPI activities, record their selection in the "IPPIs Selected" column. Identify one or more resident behaviors that are the target outcome for the intervention as indicated on the MDS Section E. Finally, note if the resident completed the project and if there were any adverse events.

Resident Unique ID#	Important Preferences	Matching IPPIs	IPPIs Selected by implementation team	Supplies Needed Location	Which targeted behavior(s) do you hope the IPPI will remediate? Check all that apply	Did the resident complete the IPPI Project? Yes No If no, why did the individual not complete the project?	Did the resident have any adverse events? Yes No If Yes, complete Serious Adverse Event Report Form
	•	•	•	○	 Physical behavioral symptom  Verbal behavioral symptom  Other behavioral symptom  Rejection of Care  Wandering  Depressive Mood Symptoms	○	○

Observation Checklist of Fidelity to IPPI Protocol conducted by Champion

Did the person delivering the IPPI do any of the following?

1. Yes No N/A Introduce self to resident
2. Yes No N/A Introduce IPPI activity to resident
3. Yes No N/A Consider possible distractions (background noise, visual/tactile)
4. Yes No N/A Check that individual could hear or was wearing hearing aids if applicable
5. Yes No N/A Interrupt resident in the middle of a visit (reverse coded)
6. Yes No N/A Give the resident a choice of two items/topics
7. Yes No N/A Ask open-ended questions
8. Yes No N/A Allow the resident time to respond to a question or complete a task
9. Yes No N/A Notice responsive behaviors (eye contact, facial expressions, gestures)
10. Yes No N/A Validate the resident's thoughts and feelings (echo words or gestures)
11. Yes No N/A Encourage the resident to do as much as possible independently
12. Yes No N/A Is the activity a positive emotional experience for the resident?
13. Yes No N/A Adapt to situation – if resident does not want to continue – change subject
14. Yes No N/A If resident becomes agitated, tries to calm them down
15. Yes No N/A Communicate that the session is over
16. Yes No N/A Thank the resident for participating
17. Yes No N/A Explain what is happening next

Serious Adverse Event Report Form Template

Protocol Title: Click or tap here to enter text.

Project ID: Click or tap here to enter text.

PI Name: Click or tap here to enter text.

Encrypted Site ID (e.g., site01, site02): Click or tap here to enter text.

Encrypted Subject ID (e.g., ptID001, ptID002): Click or tap here to enter text.

1. SAE Onset Timeframe (Two-month timeframe anytime within which the event occurred):
Click or tap to enter a date. **To** Click or tap to enter a date.

2. Duration of SAE (Number of days):
Click or tap here to enter text.

3. Location of adverse event:
 Emergency Department
 Hospital
 Outpatient visit

- Nursing Home/Skilled Nursing Facility
- Home
- Other, Specify: Click or tap here to enter text.
- Unknown

4. Was this an unexpected adverse event? Yes No

5. Brief description of participant:

Sex: Choose an item.

Age: Choose an item.

6. Adverse Event Term: Click or tap here to enter text.

7. Brief description of the nature of the serious adverse event (attach additional page if more space is needed.): Click or tap here to enter text.

8. Category of the serious adverse event:

- death
- life-threatening
- hospitalization - initial or prolonged
- disability / incapacity
- required intervention to prevent permanent impairment (Devices Only)
- important medical event

9. Intervention type:

- Behavioral/Life Style, Specify: Click or tap here to enter text.
- Device, Specify: Click or tap here to enter text.
- Education, Specify: Click or tap here to enter text.
- Medication Deprescribing, Specify: Click or tap here to enter text.
- Other, Specify: Click or tap here to enter text.

10. Intervention target:

- Clinicians/staff
- Person living with dementia
- Care partner
- Other, Specify: Click or tap here to enter text.

11. Relationship of event to intervention:

- Not related (clearly not related to the intervention)
- Possible (may be related to the intervention)
- Definite (clearly related to the intervention)

12. Was study intervention discontinued due to event? Yes No

13. What steps were taken to treat serious adverse event? If none, state so.

Click or tap here to enter text.

14. List any relevant tests, laboratory data, history, including preexisting medical conditions (do not include dates or identifiable locations):

Click or tap here to enter text.

15. Type of report: Initial Follow-up Final

Signature of Principal Investigator _____ **Date:** _____

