provided IPPI activity training videos (each 10-15 min), and be provided the IPPI manual with a checklist of steps, 60+ different IPPI protocols that address all 16 MDS 3.0 preferences in Section F, sample letters/scripts introducing the IPPI to family and staff, and communication tips sheets. Any member of the implementation team can deliver an IPPI activity. We will ask champion(s) to demonstrate an IPPI for care partners (e.g., CNAs) to watch, and then observe each care partner's initial IPPI implementation.

The champion(s) will be provided with a pragmatic data collection binder of paper forms (See Appendix A) to record these initial observations (in the form of a checklist). In addition, this binder will include a form to document staff training completion, resident preferences, and the behavior or mood item to target with the IPPI program that is most distressing to each identified eligible resident. Forms for champion(s) to document adverse events and withdraws will also be included in the binder.

Implementation team members will align stated preferences of each eligible resident with specific IPPI protocols (i.e., important preference for reading will be matched with a reading activity IPPI protocol). While any implementation team member can deliver an IPPI activity, we will encourage care partners to take the lead in implementation of the preferred IPPI activity with each enrolled resident on a regular basis. Initiation of engagement will be rolling, adding 3-7 residents per month for 3-4 consecutive months. The care partners will implement a minimum of 2 IPPI protocols per week with each resident for 6 months, to ensure continuous completion of the intervention through to the date of the resident's next two quarterly or annual MDS 3.0 assessment (3-month and 6-month follow-up data). The project manager will provide virtual coaching to communities throughout implementation as needed. Table 1 below outlines the intervention structure and implementation strategy. In addition, we identify the implementation measure/metric we will track during the course of implementation.

Table 1. IPPI Intervention Structure, Implementation Strategy, and Implementation Measures

Intervention Structure	Implementation Strategy	Implementation Measure
Establish Co-champions	Assess Organizational Readiness	Organizational Readiness for Implementing Change (ORIC) ³⁰

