6.2.2 Enrollment, Baseline, and/or Randomization

Enrollment

There will be a waiver of consent for all residents enrolled in the program. Upon identification of eligibility, the implementation team uses the Resident Preferences Worksheet to identify next steps. This will be a rolling process as individuals are identified as eligible to participate. Each enrolled individual will have a Worksheet completed at their specific time of enrollment. In this Worksheet, members of the implementation team will identify the resident's important preferences and identify matching IPPI protocols that can be used. They will also identify the behavior they hope to target with the IPPI intervention. A copy of the care plan will be obtained to ensure that the targeted behavior is addressed. The PI will collect this Worksheet from champions to determine whether or not the IPPI protocols were appropriately matched to important resident preferences as a measure of implementation fidelity every three months.

Baseline Assessments

The baseline assessment for residents will be their most recent MDS 3.0 (either

annual or quarterly). The BIMS and Section D/Section E responses will be provided to the PI for each enrolled resident by the UCH IT professionals. These data will include the targeted mood or behavior selected by care partners at enrollment. The type of mood or behavior item being targeted will be different for each resident (e.g., wandering for one, verbal behavior for another).

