6.2.4 Completion/Final Evaluation

Each enrolled resident will receive 6-months of the IPPI intervention. Upon completion of the intervention an Exit Interview will be completed with implementation team members at each NH site. Members of the implementation team will be invited to participate in a semi-structured interview with researchers at the end of the project. The Exit interview (see Appendix B) will contain open-ended questions about communication and facilitators and barriers. It will also include close-ended questions on acceptability, feasibility, and appropriateness using the Implementation Research Measure for program acceptability, appropriateness, and feasibility of Proctor et al. (2011) and Weiner et al. (2017).

7 **SAFETY ASSESSMENTS**

Once an individual is enrolled in the study, participant safety will be monitored. Enrollment is defined as a resident identified as eligible based on most recent MDS 3.0 assessments and then having a completed Resident Preferences Worksheet.

No known risks of the intervention are anticipated. The potential risks or discomfort are minimal to the organization, residents, and care partners. This intervention is focused on a positive interaction around the preference of the resident and their care partners, such as a sing-a-long activity, or going outside when the weather is good. The activities can be stopped if the resident or care partners experience distress, however that is unlikely to occur as the intervention found that residents had increased positive affect during and after the intervention. Residents can refuse to participate any time a care partner seeks to engage with them.

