The primary clinical outcome will be reports of distress as rated in the residents' MDS 3.0 annual or quarterly assessments in Section E and Section D (Saliba & Buchanan, 2009). These items will also be rated by the implementation team care partner delivering the intervention. These data will be collected at baseline (to determine eligibility) and at 3-months and 6-months post-intervention enrollment. The items in Section D and Section E are validated standardized items used to assess all NH residents in the United States receiving funding from the Centers for Medicare and Medicaid Services. Section D depression item responses are drawn from the widely used and validated PHQ-9 (Kroenke et al., 2001; anhedonia, sad mood, poor self-esteem, poor appetite, or restlessness). The items ask *“Over the past 2 weeks, have you been bothered by any of the following problems?”* and then if the resident responds “yes” they are asked *“About how often have you been bothered by this?”*. Item level scores are 0 (*did not occur*), 1 (2-6 days), 2 (7-11 days), or 3 (12-14 days). The Section E behavior items have been used as a valid indicator of behavioral distress (Saliba & Buchanan, 2009). Items include the presence of verbal, physical or other behavior symptoms directed toward others, rejection of care, and wandering. For section E, each behavior is rated with a 0 (*did not occur in the past week*), 1 (*occurred 1-3 days in the past week*), 2 (*occurred 4-6 days*) or 3 (*occurred daily*). For each resident care partners will have designated a targeted mood or behavior item selected for improvement and assessed via MDS data. The targeted mood or behavior selected by the care partner at baseline will be reassessed at 3-months and 6-months and recorded as 0 = *stayed the same as baseline* (e.g., score on MDS 3.0 baseline assessment equals score on MDS 3.0 follow-up assessment), 1 = *got better* (e.g., score on

MDS 3.0 baseline assessment is better (lower) than the score on the MDS 3.0 follow-up assessment), or 2 = *got worse* (e.g., score on MDS 3.0 baseline assessment is worse (higher) than the score on MDS 3.0 follow-up assessment) for our primary, person-centered clinical outcome. The type of mood or behavior item being tracked will be different for each resident (e.g., wandering for one, verbal behavior for another)

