9.4.1 Primary outcome

The primary clinical outcome will be reports of distress as rated in the residents' MDS 3.0 annual or quarterly assessments in Section E and Section D (Saliba & Buchanan, 2009). These items will also be rated by the implementation team care partner delivering the intervention. These data will be collected at baseline (to determine eligibility) and at 3-months and 6-months post-intervention enrollment. For each resident, a targeted mood or behavior item selected for improvement and assessed via MDS data will be used as the primary outcome. The targeted mood or behavior will be recorded as 0 = *stayed the same as baseline* (e.g., score on MDS 3.0 baseline assessment equals score on MDS 3.0 follow-up assessment), 1 = *got better* (e.g., score on MDS 3.0 baseline assessment is better (lower) than the score on the MDS 3.0 follow-up assessment), or 2 = *got worse* (e.g., score on MDS 3.0 baseline assessment is worse (higher) than the score on MDS 3.0 follow-up assessment) for our primary, person-centered clinical outcome at 3-months and 6-months post

intervention enrollment. The type of mood or behavior item being tracked will be different for each resident (e.g., wandering for one, verbal behavior for another).

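### The Resident Preferences Worksheet does not record the single MDS item that defines the primary clinical outcome for residents with several ticks, or with a mood tick and two or more non-zero mood items

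*Combined protocol and SAP*

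**What the plan says.** **The outcome is one item per resident.** Section 9.4.1: "For each resident, a targeted mood or behavior item selected for improvement and assessed via MDS data will be used as the primary outcome". Section 9.1 names the selector and the time: "The targeted mood or behavior selected by the care partner at baseline will be reassessed at 3-months and 6-months". Section 3 adds the criterion, saying that a binder form will record "the behavior or mood item to target with the IPPI program that is most distressing to each identified eligible resident".

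**The form collects something else.** The Resident Preferences Worksheet is the only binder form shown with a target field. Its instruction reads "Identify one or more resident behaviors that are the target outcome for the intervention as indicated on the MDS Section E", and its column heading reads "Which targeted behavior(s) do you hope the IPPI will remediate? Check all that apply". There are six boxes: physical, verbal and other behavioral symptoms, rejection of care, wandering, and one for depressive mood symptoms. The form does not mention the Section 3 criterion.

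**Other places where the target may be held.** Section 6.2.2 says of the data supplied by the provider's IT staff: "These data will include the targeted mood or behavior selected by care partners at enrollment". Section 10.1 places the primary clinical outcome in the MDS assessments held in the EMR and lists the worksheet under feasibility and fidelity. Table 1 and Section 6.2.2 also look for the target in the care plan.

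**Analysis.** Section 6.2.3 scores change in each Section D and E item at 3 months. Section 9.5 refers to targeted behaviors in the plural, coded in two ways, and reports the percentages improved, unchanged and worsened.

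**The concern.** A single-item outcome can be computed only if the item is recorded. The worksheet can be filled in correctly and still not record it, so this is a mismatch between form and protocol, not a matter of staff error.

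For the affected residents someone must later decide which item counts, or how several items reduce to one category. Section 6.2.1 sends MDS data to the principal investigator only once all enrolled residents are past 3 months, so baseline and 3-month scores arrive together. Section 16 has the binder forms submitted with the 3- and 6-month electronic data. If the gap is not noticed sooner, the decision could be taken with follow-up scores in view.

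At stake is the meaning of the main clinical percentage. It comes from a pilot whose findings, under Section 9.2, are to guide the approach and power of a full-scale trial.

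**Working it through.** The plan states no figure for this outcome (no expected improvement rate, power or alpha), so there is nothing to reproduce. The check has two parts.

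**1. Which completed worksheets identify the item?** Section 9.1 lists five Section E behaviors, which match the five behavior boxes one to one. It lists five Section D items (anhedonia, sad mood, poor self-esteem, poor appetite, restlessness), which share one box. Each item is scored 0 to 3, so an item scored 0 at baseline cannot improve.

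| Worksheet entry | Is the item identified? |
|---|---|
| One behavior tick | Yes |
| Mood tick only, one non-zero Section D item at baseline | Yes, in practice, from the linked baseline MDS |
| Mood tick, two or more non-zero Section D items | No |
| Two or more ticks | No |

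**2. How much could it matter?** This is an illustration. Only the 108 residents (Précis, Design and Outcomes) come from the documents. Assumed: each item improves with probability q = 0.30; items share a latent normal correlation of 0.5; 10%, 25% or 50% of residents have two ticks.

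Formulas, with Φ₂ the bivariate normal distribution function and z = Φ⁻¹(q):
- All items improve: Φ₂(z, z; 0.5) = 0.157.
- At least one improves: 2q − 0.157 = 0.60 − 0.157 = 0.443.
- One item fixed in advance: q = 0.300.

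The departure from the protocol's single-item rule is 0.443 − 0.300 = 0.143 upward, or 0.300 − 0.157 = 0.143 downward.

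| Share with two ticks | Residents: 0.143 × 108 × share | Shift in overall percentage: 14.3 × share |
|---|---|---|
| 10% | 1.5 | 1.4 points |
| 25% | 3.9 | 3.6 points |
| 50% | 7.7 | 7.2 points |

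*Sensitivity.* With q from 0.2 to 0.4, correlation from 0.3 to 0.7 and the same shares, the smallest departure is (0.287 − 0.200) × 108 × 0.10 = 0.9 residents (q = 0.2, correlation 0.7). The largest is (0.594 − 0.400) × 108 × 0.50 = 10.5 (q = 0.4, correlation 0.3).

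*Mood tick covering three non-zero items (also assumed), q = 0.30, correlation 0.5.* At least one improves: 0.530; all three improve: 0.101. At shares of 10%, 25% and 50%, the any-item rule departs from 30% by 0.230 × 108 × share = 2.5, 6.2 and 12.4 residents. The all-items rule departs by 0.199 × 108 × share = 2.1, 5.4 and 10.7.

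**The case against.** The strongest reply is that the body of the protocol is complete. It gives one item, a selector, a time and a criterion, and a one-item outcome needs no combining rule. **This stands.** A reader might infer that the plan lacks a rule for combining several targets. The documents do not support that: what is missing is a form that records the item already specified.

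Second, the worksheet may not be the source for the outcome at all, since Sections 6.2.2 and 10.1 point to the IT and EMR data. This stands in part. It is too strong to say that no source exists; several are named. But no EMR field holding a single item is described, Section 6.2.2 also has the target identified on the worksheet, and no source is given precedence.

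Third, a reader might infer that targets can be picked after the results are known. The ticks themselves are fixed early: "Enrollment is defined as a resident identified as eligible based on most recent MDS 3.0 assessments and then having a completed Resident Preferences Worksheet". Section 6.2.2 has worksheets collected every three months and Section 10.3.5 has forms reviewed every three months, so gaps could be queried before the half-way transfer. What remains is that nothing requires this, and Section 16 allows the forms to arrive with the follow-up data.

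Fourth, setting an any-item rule against an all-items rule gives 44% versus 16%, or about 3, 8 and 15 residents at the three shares. The documents propose neither rule. The relevant yardstick is the single item, which halves those counts. If both items have the same improvement rate, choosing either one without regard to follow-up leaves the expected percentage at 30%.

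Fifth, the wording in Section 9.5 is weak evidence of several targets. Sections 9.1 and 9.4.1 say that care partners will also rate these items, so the two ways may mean MDS and care-partner coding.

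**Conclusion.** The point holds for two groups: residents with two or more ticks, and residents with a mood tick and at least two non-zero Section D items at baseline. For them the worksheet does not identify the primary outcome item, and no other source is described as holding it or said to govern.

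The affected share is not in the documents and may be zero. Under the assumptions above, with two ticks, the reported count improved would depart from the single-item result by about 1.5, 4 or 8 of 108 residents, and by roughly 1 to 10 over the wider range tried. These are illustrations, not estimates.

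It would be wrong to infer an inflated type I error or lost data. Sections 9.4 and 9.5 make the resident analysis descriptive, and Section 10.2 extracts the Section D and E scores. Feasibility and fidelity, which Section 9.1 links to the main purpose of the pilot, are unaffected. This should be fixed, at the lower end of that grade.

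**What to change.** 1. **Form.** Add one mandatory worksheet field, completed at enrollment, that names exactly one of ten listed items (five from Section D, five from Section E) by the Section 3 criterion. Correct the instruction to cover both sections, state that this field governs the primary outcome, and treat any other ticks as secondary.
2. **Residents already enrolled whose item is not identified.** Ask the provider's IT office whether the extract holds a single target item; if it does, use it. Otherwise query the site champion during the three-monthly form review (Section 10.3.5), before the half-way MDS transfer (Section 6.2.1). Site staff may already have seen a 3-month assessment, so label these cases retrospective. Do not default to the highest baseline score across sections: Section 9.1 rates behaviors over one week (a zero means "did not occur in the past week") and mood items over two. Where no item can be named, report any-item, all-items and per-item results, labelled as such.
3. **Text.** Align Sections 6.2.3, 9.1, 9.4.1 and 9.5 on one item per resident.

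**Cost.** One form change, wording edits in four sections, a query to site champions, and IRB review of the modification (Section 11.1). No extra resident assessments are needed.
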